8.0 Study Monitoring and Auditing

Investigator responsibilities

Investigator responsibilities are set out in the ICH guideline for Good Clinical Practice (GCP) and in the US Code of Federal Regulations.

Investigators must enter study data into MDACC's PDMS. The Investigator will permit study-related monitoring visits and audits by MDACC's ORERM, Celgene, or its representatives, IRB/EC review, and regulatory inspection(s) (e.g., FDA, EMEA, TPP), providing direct access to the facilities where the study took place, to source documents, to CRFs, and to all other study documents.

The Investigator, or a designated member of the Investigator's staff, must be available at some time during monitoring visits to review data and resolve any queries and to allow direct access to the subject's records (e.g., medical records, office charts, hospital charts, and study related charts) for source data verification. The data collection must be completed prior to each visit and be made available to MDACC ORERM and the Celgene representative so that the accuracy and completeness may be checked.

Regulatory Considerations / Institutional Review Board/Ethics Committee approval

The protocol for this study has been designed in accordance with the general ethical principles outlined in the Declaration of Helsinki. The review of this protocol by the IRB/EC and the performance of all aspects of the study, including the methods used for obtaining informed consent, must also be in accordance with principles enunciated in the declaration, as well as ICH Guidelines, Title 21 of the Code of Federal Regulations (CFR), Part 50 Protection of Human Subjects and Part 56 Institutional Review Boards.

The Investigator will be responsible for preparing documents for submission to the relevant IRB/EC and obtaining written approval for this study. The approval will be obtained prior to the initiation of the study.

The approval for both the protocol and informed consent must specify the date of approval, protocol number and version, or amendment number.

Any amendments to the protocol after receipt of IRB/EC approval must be submitted by the Investigator to the IRB/EC for approval. The Investigator is also responsible for notifying the IRB/EC of any serious deviations from the protocol, or anything else that may involve added risk to subjects.

Any advertisements used to recruit subjects for the study must be reviewed and approved by the IRB/EC prior to use.

Informed consent

The Investigator must obtain informed consent of a subject or his/her designee prior to any study related procedures as per GCPs as set forth in the CFR and ICH guidelines.

Documentation that informed consent occurred prior to the subject's entry into the study and the informed consent process should be recorded in the subject's source documents. The original consent form signed and dated by the subject and by the person consenting the subject prior to the subject's entry into the study, must be maintained in the Investigator's study files.

Study records requirements

The Investigator must ensure that the records and documents pertaining to the conduct of the study and the distribution of the study drug, that is copies of CRFs and source documents (original documents, data, and records [e.g., hospital records; clinical and office charts; laboratory notes; memoranda; subject's diaries or evaluation checklists; pharmacy dispensing records; recorded data from automated instruments; copies or transcriptions certified after verification as being accurate copies; microfiches; photographic negatives, microfilm, or magnetic media; x-rays; subject files; and records kept at the pharmacy, at the laboratories, and at medico-technical departments involved in the clinical study; documents regarding subject treatment and study drug accountability; original signed informed consents, etc.]) be retained by the Investigator for as long as needed to comply with national and international regulations (generally 2 years after discontinuing clinical development or after the last marketing approval). The Investigator agrees to adhere to the document/records retention procedures by signing the protocol.

Premature discontinuation of study

Single center

The responsible local clinical Investigator as well as Celgene have the right to discontinue this study at any time for reasonable medical or administrative reasons in any single center. Possible reasons for termination of the study could be but are not limited to:

- Unsatisfactory enrollment with respect to quantity or quality.

- Inaccurate or incomplete data collection.
- Falsification of records.
- Failure to adhere to the study protocol.

Study as a whole

Celgene reserves the right to terminate this clinical study at any time for reasonable medical or administrative reasons.

Any possible premature discontinuation would be documented adequately with reasons being stated, and information would have to be issued according to local requirements (e.g., IRB/EC, regulatory authorities, etc).

Patients will be given instructions and the M.D. Anderson contact name (principal investigator/MD Anderson Leukemia staff treating physician), phone, and fax numbers. The referring oncologist will be identified, contacted, and the protocol details discussed.

All therapy will be given under the care of MD Anderson Leukemia staff treating physician. The referring oncologist should contact the MD Anderson Leukemia staff treating physician with any questions or problems and the modifications should be initiated only by the MD Anderson Leukemia staff treating physician or principal investigator, and complications will be recorded in a progress note at each follow-up visit.

From past experience, it is recognized collaboration with oncologist outside MD Anderson may occasionally result in some difficulties such as 1) not performing tests as required, 2) not sending results of tests or updates of patient condition, 3) and not informing on toxicities and hospitalizations. Therefore: 1) we will discuss with the referring oncologist about the protocol and doses, 2) we will make significant efforts (contact at least twice and document) to retrieve the information (tests, toxicities, hospitalizations), and 3) we will record in a progress note all the information on follow-up visits. Since information may still be missing in one or more components in some patients (e.g. missing once CBC), these types of difficulties will be collected and documented as protocol deviations.

9.0 STATISTICAL CONSIDERATIONS

The primary objective of phase II of this study is to assess efficacy in terms of the objective response rate (complete and partial response, and clinical improvement) with lenalidomide and prednisone in patients with MF. The MinMax two-stage design proposed by Simon will be implemented. Sample size and decision criteria are chosen to reduce the expected accrual if the treatment

is ineffective in regard to response relative to having no interim stopping rule. The target response rate is 35%. A response rate of 20% or less will be considered unacceptable and treatment with the therapy will be discontinued. Given the response rates stated above, if the probability of inappropriately accepting a poor therapy is 10%, a total sample size of 41 patients will result in 80% power.

In the first stage of the design, a total of 22 patients will be enrolled and the study will be put on hold to assess response. If four or fewer patients respond to the combination therapy, after being treated for 6 months, then the study will be terminated and the therapy will be declared ineffective. However, as soon as 5 or more patients respond to the lenalidomide, an additional 19 patients will be enrolled to complete the study.

After a total of 41 patients have been enrolled into the study, if eleven or fewer patients respond to the therapy, the therapy will be declared ineffective. However, if greater than 11 patients respond to the therapy, the therapy will be considered efficacious. The probability of early termination due to unacceptable response rate is 54%.

Descriptive statistics will be utilized to assess response, time to response, and response duration. Responses will be categorized as the best response achieved during the course of the study. Time to response is defined as the time from start of therapy until the response criteria are fulfilled. Response duration will be defined as the time from response until relapse (progressive disease) or death.

The safety analysis will include subjects who are enrolled to treatment and take at least one dose of study medication. Toxicity will be graded according to the NCI criteria. Descriptive statistics will be used to describe adverse events related to the study drug. Adverse events will be listed and tabulated.

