- Complete resolution of disease-related symptoms and signs including palpable hepatosplenomegaly.
- Peripheral blood count remission defined as hemoglobin > 11 g/dL, platelet count $\geq 100 \times 10^9/L$, and absolute neutrophil count $\geq 1.0 \times 10^9/L$.
- Normal leukocyte differential including disappearance of nucleated red blood cells and immature myeloid cells in the peripheral smear, in the absence of splenectomy.*
- Bone marrow histological remission defined as the presence of age-adjusted normocellularity, < 5% myeloblasts, and an osteomyelofibrosis grade of ≤ 1 .**

Partial remission (PR): Requires all of the above criteria for CR except the requirement for bone marrow histological remission. However, a repeat bone marrow biopsy is required in the assessment of PR and may or may not show favorable changes that do not however fulfill criteria for CR.

Clinical improvement (CI): Requires one of the following in the absence of both disease progression (as outlined below) and CR/PR assignment (*CI response is validated only if it lasts for ≥ 8 weeks*).

- A ≥ 2 g/dL increase in hemoglobin level or becoming transfusion independent (applicable only for patients with baseline hemoglobin level of < 10 g/dL).[§]
- Either a $\geq 50\%$ reduction in palpable splenomegaly of a spleen that is ≥ 10 cm at baseline or a spleen that is palpable at > 5 cm at baseline becomes not palpable.^{§§}
- A $\geq 100\%$ increase in platelet count and an absolute platelet count of $\geq 50,000 \times 10^9/L$. (applicable only for patients with baseline platelet count of < $50 \times 10^9/L$).
- A $\geq 100\%$ increase in ANC and an ANC of $\geq 0.5 \times 10^9/L$ (applicable only for patients with baseline absolute neutrophil count of < $1 \times 10^9/L$).

Progressive disease: Requires one of the following;[¶]

- Progressive splenomegaly that is defined by the appearance of a previously absent splenomegaly that is palpable at > 5 cm below the left costal margin or a $\geq 100\%$ increase in palpable distance for baseline splenomegaly of 5-10 cm or a $\geq 50\%$ increase in palpable distance for baseline splenomegaly of > 10 cm.
- Leukemic transformation confirmed by a bone marrow blast count of $\geq 20\%$.
- An increase in peripheral blood blast percentage of $\geq 20\%$ that lasts for ≥ 8 weeks.

Stable disease: None of the above.

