Relapse: Loss CR, PR, and CI. In other words, a patient with CR or PR is considered to have undergone relapse when he or she no longer fulfils the criteria for CI.

**Because of subjectivity in peripheral blood smear interpretation, CR does not require absence of morphological abnormalities of red cells, platelets, and neutrophils.*

*** In patients with CR, a complete cytogenetic response is defined as failure to detect a cytogenetic abnormality in cases with a pre-existing abnormality. A partial cytogenetic response is defined as 50% or greater reduction in abnormal metaphases. In both cases, at least 20 bone marrow- or peripheral blood-derived metaphases should be analyzed. A major molecular response is defined as the absence of a specific disease-associated mutation in peripheral blood granulocytes of previously positive cases. In the absence of a cytogenetic/molecular marker, monitoring for treatment-induced inhibition of endogenous myeloid colony formation is encouraged. Finally, baseline and post-treatment bone marrow slides are to be stained at the same time and interpreted at one sitting by a central review process.*

§Transfusion dependency is defined by a history of at least 2 units of red blood cell transfusions in the last month for a hemoglobin of < 8.5 g/dL that was not associated with clinically overt bleeding. Similarly, during protocol therapy, transfusions for a hemoglobin of \geq 8.5 g/dL is discouraged unless it is clinically indicated.

§§In splenectomized patients, palpable hepatomegaly is substituted with the same measurements.

¶It is acknowledged that worsening cytopenia might represent progressive disease but its inclusion as a formal criterion was avoided because of the difficulty distinguishing disease-associated from drug-induced myelosuppression. However, a decrease in hemoglobin of \geq 2 g/dL, a 100% increase in transfusion requirement, and new development of transfusion dependency, each lasting for more than 3 months after the discontinuation of protocol therapy can be considered disease progression.

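### Section 9.0 ends response duration at relapse, glossed as progressive disease, but section 6.0 defines these as different events, so a lost response could go on counting

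*Combined protocol and SAP*

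**What the plan says.** Section 9.0 defines the endpoint in one sentence: "Response duration will be defined as the time from response until relapse (progressive disease) or death". It is to be summarised descriptively.

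Section 6.0 gives two sets of response criteria. The standard set defines CR, PR and HI (hematological improvement) and contains no definition of relapse or progression. The international working-group set, which the study will attempt to validate, defines CR, PR, CI (clinical improvement), progressive disease and relapse:

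- **Relapse** is loss of CR, PR and CI: "a patient with CR or PR is considered to have undergone relapse when he or she no longer fulfils the criteria for CI".
- **Progressive disease** needs one of three things: spleen growth past set palpation limits, marrow blasts of at least 20%, or a blood-blast increase of at least 20% lasting at least 8 weeks.
- **Cytopenia** is addressed in a footnote: "worsening cytopenia might represent progressive disease but its inclusion as a formal criterion was avoided". The same footnote allows an exception for a hemoglobin fall, a doubled transfusion requirement or new transfusion dependency, "each lasting for more than 3 months after the discontinuation of protocol therapy can be considered disease progression".
- **CI** can be assigned only "in the absence of both disease progression (as outlined below) and CR/PR assignment".

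Section 5.10 lists documented progression and losing a response as alternative reasons to stop therapy. Section 1.2 names hematological improvement as part of the primary objective; section 9.0 names clinical improvement in its place.

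**The concern.** The bracketed words in section 9.0 equate two events that section 6.0 keeps apart and that section 5.10 lists as alternatives. No section says which of the two ends the response. If the bracketed words are taken as the definition, a patient whose response has gone but who has not met a spleen or blast criterion is still counted as responding until progression or death.

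Response duration is the only durability measure in section 9.0, so this decides how lasting the benefit appears. The stakes are limited, because duration is not among the section 1.2 objectives and carries no target or test.

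**Working it through.** **The plan's own figures.** Section 9.0 states no figure for response duration. Its design figures reproduce, with 22 patients in stage 1, 19 in stage 2, a stop at 4 or fewer responses, and efficacy declared at 12 or more of 41:

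- Early termination at 20%: P(X1 ≤ 4 | 22, 0.20) = 0.543 (stated 54%).
- Type I error: sum over x1 ≥ 5 of P(X1 = x1 | 22, 0.20) × P(X2 ≥ 12 − x1 | 19, 0.20) = 0.096 (stated limit 10%).
- Power: the same sum at 0.35 = 0.804 (stated 80%).

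All three depend on whether a patient responds, not on when the response ends, so this point leaves them unchanged.

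**Can a response be lost without progression?** The working-group set has four CI routes. The neutrophil route needs a baseline ANC below 1 × 10⁹/L, while section 4.1 requires at least 1 × 10⁹/L at entry, so that route is closed. Three remain.

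| Route | Response is lost when | Formal progression on treatment |
|---|---|---|
| Hemoglobin or transfusion | the gain or the independence is no longer met | none; only the discretionary off-therapy exception |
| Platelets | the doubling or the minimum count is no longer met | none; the exception does not mention platelets |
| Spleen | the reduction is no longer met | set growth limits, worked below |

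*Spleen, 50% route* ("reduction in palpable splenomegaly of a spleen that is" at least 10 cm). Take a 12 cm spleen.
- Response requires 0.5 × 12 = 6 cm or less, so it is lost above 6 cm.
- Progression with the pre-treatment baseline (band above 10 cm, 50% increase): 1.5 × 12 = 18 cm.
- Progression with the on-treatment 6 cm as baseline (5–10 cm band, 100% increase): 2 × 6 = 12 cm.
- Regrowth to 11 cm is therefore loss without progression on either reading.

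*Spleen, not-palpable route* ("a spleen that is palpable at > 5 cm at baseline becomes not palpable"). Take an 8 cm spleen that became not palpable.
- Response is lost once it can be felt again.
- Progression needs more than 5 cm if the reappearance counts as "the appearance of a previously absent splenomegaly that is palpable at > 5 cm below the left costal margin".
- With the pre-treatment baseline it needs 2 × 8 = 16 cm.
- Reappearance at 3 cm is loss without progression on either reading.

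**Direction, working-group set.** CI requires absence of progression, so any progression ends CI and is also a relapse. Relapse can come without progression. Hence time to relapse ≤ time to progression, and the progression reading gives a duration that is equal or longer.

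**Direction, standard set.** HI has no absence-of-progression clause. A patient who keeps a hemoglobin HI while the spleen passes a progression limit progresses before losing the response; a patient who loses that HI with a stable spleen does the reverse. Either order is possible, so no direction follows.

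**Illustration only; every input is assumed.** Take an exponential time to loss of response with a 12-month median (a = ln2/12). Let a share p of responders lose the response before progression or death, with a further exponential lag to that event (b = ln2/median lag), and let every later event be observed. The median t under the progression reading solves

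(1 − p)·exp(−at) + p·[b·exp(−at) − a·exp(−bt)]/(b − a) = 0.5,

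where the bracketed ratio becomes exp(−at)(1 + at) when the lag median is also 12 months.

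- p = 0.10, lag 1 month: 12.2 months.
- p = 1/3, lag 6 months: 15.1 months.
- p = 2/3, lag 12 months: 23.0 months.

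For scale, the target rate gives 0.35 × 41 = 14.35 responders. With 14 events, a 95% exponential interval around a 12-month median is 12 × 28/44.46 to 12 × 28/15.31, or 7.6 to 21.9 months.

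**The case against.** The strongest reply is that the operative word in section 9.0 is relapse, which section 6.0 defines as loss of CR, PR and CI. If that definition governs, duration ends when the response is lost and nothing is overstated. This stands as a limit: the overstatement arises only if the bracketed words govern. It does not remove the defect, because those words give relapse a meaning that contradicts section 6.0, and no section says which prevails.

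A second reply is that both definitions belong to the supplementary criteria, while the standard set is the one section 6.0 says will be applied. This also stands in part. A reader might infer that the bracketed words can never shorten duration; that holds for the working-group set only. If HI governs, the problem is a missing definition rather than a contradiction.

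A third reply is that patients stop therapy on losing a response anyway. Section 5.10 governs treatment; it does not say on what date the response ends for analysis.

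Two further inferences are not supported. Two of three usable CI routes lacking an on-treatment progression criterion is a count of criteria, not a share of responders. The month figures above are not a forecast: the documents support none of their inputs, and dating or censoring after loss of response is unstated.

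**Conclusion.** The rule is wrong as written: it names one event by two terms that the same document defines differently. Under the working-group criteria, if the bracketed words govern, reported duration equals or exceeds the time to loss of response. If the standard criteria govern, the end of response is undefined and no direction can be claimed.

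The size cannot be derived from the documents. A reader might infer that this trial's durations will be overstated, but that would need evidence that the bracketed words will be followed and that responses are in fact lost before progression; the documents give neither. The consequence is confined to a descriptive measure. This is a correction that should be made, at modest weight.

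**What to change.** Delete the bracketed words in section 9.0 and end the definition as follows: *…until the earliest of loss of response (relapse as defined in section 6.0), progressive disease as defined in section 6.0, or death; responses still ongoing are censored at the last assessment.*

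State that the criteria set used for the primary endpoint determines loss of response, and reconcile hematological improvement in section 1.2 with clinical improvement in section 9.0. If CI applies, the existing relapse definition is enough. If HI applies, add: *loss of response means no longer meeting any CR, PR or HI criterion of the standard set.*

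Leave the start of duration and the section 5.10 discontinuation criteria as they are. The cost is one sentence of wording, or two if HI applies, plus the statement on the criteria set. It uses blood counts, transfusion records and spleen measurements already collected. The downside is that reported durations may be shorter.

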10.0 CORRELATIVE STUDIES

Correlative studies will be done pre-therapy and then every 3 months until patient completes 24 cycles, then every 6 months while on therapy. In the peripheral blood and bone marrow aspirate we will measure the levels of TGF-beta, bFGF, and PDGF. Attempt will be made to collect all samples, but it is possible that some samples might be missed. These tests will be done at M.D. Anderson, in the laboratory of [name]. For the testing in blood samples, 10cc purple top tube will be obtained and for the testing in bone marrow aspirate samples, 3cc purple top tube will be obtained.

In addition, the analysis of total and phosphorylated c-Jun protein in peripheral blood will be done. Sample processing will be performed in the laboratory of [name] at MD Anderson, while sample analysis will take place at

the Celgene Corporation. Samples will be obtained pre-therapy, after 6 and 18 months of therapy. Not all samples might be obtained at all time points. Peripheral blood will be collected into 2 specialized CPT 8 mL vacutainer tubes. Peripheral blood mononuclear cells (PBMC) will be separated, pelleted, lysed, and stored frozen at -70° C until shipping. Samples will be coded so that patient confidentiality will be preserved. They will be shipped on dry ice to the Celgene Corporation, San Diego. Contact person is: [name], Celgene, [name], [contact], Email: [contact] (see Appendix I)

